6.1. Safety endpoints

- Adverse reactions: Adverse events determined to be related to Lyrica by the investigator or the sponsor
- Adverse events: All-causality adverse events
- Serious adverse reactions or adverse events: Adverse reactions or adverse events determined to be serious by the investigator or the sponsor
- Major investigation items:
 - Peripheral edema and edema-related events*
*: Adverse events of the cardiovascular and respiratory systems will also be checked.
 - Dizziness, somnolence, loss of consciousness, syncope, and potential for accidental injury

- Vision-related events

Events to be handled as major investigation items are defined as events of safety specification in the European risk management plan of Lyrica (important identified risk: peripheral edema and edema-related events; dizziness, somnolence, loss of consciousness, syncope, and potential for accidental injury; vision-related events).

- Accident-related events:

Accident-related events are defined as events coded to the MedDRA SMQ “accidents and injuries”. These events will be evaluated for adverse events.

- Pancreas-related events:

Pancreas-related events are defined as events coded to the MedDRA SMQ “acute pancreatitis (narrow scope)”, those coded to the MedDRA HLGT “exocrine pancreas conditions” or the MedDRA HLT “pancreatic neoplasms malignant (excl islet cell and carcinoid)”, and those related to the laboratory test results of primary pancreatic parameters of serum amylase, lipase, and trypsin among those coded to the MedDRA SOC “Investigations”.

- Thyroidal function-related events:

Thyroidal function-related events are defined as events coded to the MedDRA SMQ “thyroid dysfunction”.

- Change in appetite and activity-related events

Change in appetite and activity-related events are defined as events coded to the MedDRA PT “decreased activity”, “decreased appetite”, “increased appetite”, or “hypokinesia”.

- Euphoric mood-related events:

Euphoric mood-related events are defined as events coded to the MedDRA PT “euphoric mood”.

- Suicide-related events:

Suicide-related events are defined as events coded to the MedDRA SMQ “suicide/self-injury”. These events will also be evaluated for adverse events.

- Withdrawal symptom and rebound phenomenon-related events:

Withdrawal symptom and rebound phenomenon-related events are defined as events reported in patients with clinical findings at the completion of treatment of “yes” or events with the verbatim term of “withdrawal symptom and rebound phenomenon” reported.

Final identification of these events will be based on other background information available from patients experiencing the event.

- Skin disorder-related events:

Skin disorder-related events are defined as events coded to the MedDRA SOC “Skin and subcutaneous tissue disorders”.

- Body weight:

Events coded to the MedDRA PT “weight increased” are defined as events that should be investigated in the survey. Measurement values of body weight will also be evaluated.

- Laboratory parameters:

- Serum creatinine, serum amylase, serum total thyroxine (T4), thyroid-stimulating hormone (TSH), fasting blood glucose, HbA1c

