**(2) Clinical findings**

The following information will be entered about the clinical findings before the start of treatment (including the first day of treatment) and during the period from the start of treatment to the day of safety evaluation. In cases where treatment has been completed or discontinued before Week 13, the data at the time of completion (discontinuation) of treatment will be entered. If the investigator considers that the change in any of the clinical findings from the pre-treatment status is abnormal, it will be reported as an adverse event.

**(2)-1 Information before the start of treatment (including the first day of treatment) and during the period from the start of treatment to the day of safety evaluation**

[Presence/absence of peripheral edema or edema in general]\*, [Presence/absence of dizziness, somnolence, loss of consciousness, syncope and potential for accidental injury], [Presence/absence of ophthalmological abnormalities], [Presence/absence of suicidal ideation (including suicide attempt and suicide after start of treatment)], [Presence/absence of pathologic changes in appetite and activity]

**Supplementary note\***: In cases where peripheral edema or edema in general is found, adverse events of the cardiovascular and respiratory systems also need to be checked. If any clinically significant change from the pre-treatment condition is found, it should be entered in detail in the field for adverse events.

**(2)-2 Information in cases of completed (discontinued) treatment with the product (information on the day of safety evaluation following 7-day period after the day of discontinuation [including Day 7 of this period])**

[Presence/absence of withdrawal symptom/rebound phenomenon]

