The target sample size is 3400 patients with neuropathic pain in total, including 3000 patients with peripheral neuropathic pain (1000 patients with postherpetic neuralgia, if possible, and 2000 patients with peripheral neuropathic pain of the types other than postherpetic neuralgia), and 400 patients with central neuropathic pain (300 patients with post-stroke pain, if possible, and other patients with pain following traumatic spinal cord injury and pain due to Parkinson's disease). For peripheral neuropathic pain, approximately 100 each of patients should be accumulated, if possible, for trigeminal neuralgia, peripheral entrapment neuropathy, iatrogenic neuropathy, neuropathy due to tumor-induced nerve compression or infiltration, posttraumatic pain, and chronic cauda equina syndrome.

The target sample size of 3400 patients with neuropathic pain is expected to have a 97% probability to detect adverse reactions occurring at the incidence of 0.1% or higher in at least 1 patient. Of the adverse reactions included in the major investigation items, vision-related events are anticipated to develop at the lowest incidence during the survey. In

clinical studies of Lyrica conducted in Japan and overseas, the lower bound of the 95% confidence interval for the incidence of this adverse reaction was 6.70% (incidence 7.40%, 380/5134 patients). If this adverse reaction develops at the same incidence as in these clinical studies, this reaction is expected to occur in 227 or more of 3400 patients. Since the safety and efficacy of Lyrica should be evaluated in patients with each type of neuropathic pain, enrollment of the following number of patients will be ensured; approximately 100 patients each, if possible, for trigeminal neuralgia, peripheral entrapment neuropathy, iatrogenic neuropathy, neuropathy due to tumor-induced nerve compression or infiltration, posttraumatic pain, and chronic cauda equina syndrome, approximately 300 patients for post-stroke pain, and a certain number of patients for pain following traumatic spinal cord injury and pain due to Parkinson's disease.

This sample size will also allow for adequate evaluation of the characteristics of other adverse reactions included in the major investigation items. The characteristics to be evaluated include time of onset and duration of adverse reactions, and these were also investigated in the clinical studies.

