8.2.3. Safety analysis

8.2.3.1. Adverse reactions

- All adverse reactions**

Number and proportion of patients with adverse reactions will be tabulated by SOC and PT.

- Serious adverse reactions**

Number and proportion of patients with serious adverse reactions will be tabulated by SOC and PT.

- Details of adverse reactions**

Number and proportion of patients with adverse reactions will be tabulated by SOC and PT for each of the following items.

- Seriousness [Serious, non-serious]
- Expected/unexpected [expected, unexpected]
- Number of days to onset [≤ 4 weeks, >4 to ≤ 13 weeks, >13 weeks]
- Action taken [discontinuation, dose interruption or reduction, dose increase]
- Outcome [not recovered, recovered with sequelae, recovering, resolved/recovered, unknown]

If the same adverse reaction (the same PT) occurs more than once in the same patient, tabulation of the number of patients experiencing the adverse reactions will be handled as follows.

- Seriousness: Serious if both serious and non-serious reactions occurred
- Expected/unexpected: Unexpected if both expected and unexpected reactions occurred
- Number of days to onset: Number of days to onset of the first reaction
- Action taken: If more than one action were taken, select one action in the following order of priority: discontinuation, dose interruption or reduction, dose increase, none
- Outcome: Outcome of the reaction lastly occurred in the patient

- Major investigation items**

Number and proportion of patients will be calculated for the following major investigation items.

- Peripheral edema and edema-related events*^a
*: Adverse events of the cardiovascular and respiratory systems will also be checked.
- Dizziness, somnolence, loss of consciousness, syncope, and potential for accidental injury
- Vision-related events

Furthermore, number and proportion of patients with major investigation items will be tabulated for each SOC and PT by seriousness, action taken and outcome.

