For “peripheral edema and edema-related events”, number and proportion of patients with events will be tabulated by presence or absence of weight increase. Two types of definitions of patients with weight increase are used: 1) those with “weight increased (MedDRA PT)” reported as an adverse reaction; 2) those with body weight increased by 7% or more from baseline at least once. Number and proportion of patients with adverse reactions will be tabulated for each SOC and PT by presence or absence of peripheral edema. In addition, number and proportion of patients with the following adverse reactions will be tabulated by presence or absence of peripheral edema to evaluate the relationship between peripheral edema and cardiovascular and respiratory events.

- Events coded to the MedDRA PT “arrhythmia”, “atrial fibrillation”, “cardiovascular disorder”, “cardiac failure congestive”, “hypertension”, “hypotension”, “palpitations”, “tachycardia”, or “dyspnoea”
- Events coded to the MedDRA SOC “Cardiac disorders”, “Vascular disorders”, or “Respiratory, thoracic and mediastinal disorders”

For “dizziness, somnolence, loss of consciousness, syncope, and potential for accidental injury”, number of days to onset will be tabulated using more specific categories (≤ 4 weeks [1 to 28 days], 1 to 7 days, 8 to 14 days, 15 to 21 days, 22 to 28 days; >4 weeks [≥ 29 days], >4 to ≤ 13 weeks, >13 weeks). In addition, number and proportion of patients with adverse reactions will be tabulated by factor specified in Section 5.4. Tests specified in Section 8.1.3 will be performed to evaluate the relationship between patient demographics, etc. and development of adverse reactions.

Moreover, the median number of days to onset will be tabulated for the following adverse reactions.

- Dizziness
- Somnolence

^a: Occurrence of cardiovascular and respiratory events will be examined in patients with peripheral edema and edema-related events.

- Peripheral edema and edema-related events
- **Pancreas-related events, thyroidal function-related events, change in appetite and activity-related events, suicide-related events, withdrawal symptom and rebound phenomenon-related events, and skin disorder-related events**

Number and proportion of patients will be calculated for each event.

- **Patients with special background**

Number and proportion of patients with adverse reactions and serious adverse reactions will be calculated by SOC and PT in the following subgroups and other patients.

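### The SAP's appetite-and-activity endpoint counts appetite changes in both directions but activity changes only as decreases, which is narrower than the undirected protocol item

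*SAP*

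**What the plan says.** Protocol 6.4 (2), Clinical findings, includes the item "Presence/absence of pathologic changes in appetite and activity", to be recorded before treatment and up to the day of safety evaluation. The same item stands in the observation schedule in Protocol 6. Neither place gives a direction for appetite or for activity. The protocol also sets the route from finding to event: a departure from the patient's condition before treatment that the investigator judges abnormal is to be entered as an adverse event.

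SAP 6.1 keeps an undirected name for the endpoint but defines it by four MedDRA PTs: "Change in appetite and activity-related events are defined as events coded to the MedDRA PT “decreased activity”, “decreased appetite”, “increased appetite”, or “hypokinesia". The list is closed; no standardised query, higher-level term or open-ended wording extends it.

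SAP 8.2.3.1 groups this endpoint with the pancreatic, thyroid, suicide, withdrawal/rebound and skin groupings and asks for one output: "Number and proportion of patients will be calculated for each event". The same section also has a general table: "Number and proportion of patients with adverse reactions will be tabulated by SOC and PT".

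**The concern.** A patient whose activity becomes abnormally raised during treatment fits the protocol item as worded, and the investigator is told to report the change. If the event is judged related to the product, it is an adverse reaction of the kind that the endpoint's name describes. Yet it cannot enter the endpoint, because none of the four terms describes raised activity.

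What is at stake is the meaning of one reported figure. A reader who sees a number and proportion for changes in appetite and activity will take it to cover changes in both directions, as it does for appetite. For activity it would be a count of decreases under a broader label. This count is the only analysis in the SAP dedicated to that protocol item, so no other output for the item corrects the impression.

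**Working it through.** The point concerns a definition, so the main check sets the texts side by side.

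**Step 1. Classify the four listed terms by domain and direction (SAP 6.1).**

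- Appetite, decrease: 1 term (decreased appetite)
- Appetite, increase: 1 term (increased appetite)
- Activity, decrease: 2 terms (decreased activity, hypokinesia)
- Activity, increase: 0 terms

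Total 1 + 1 + 2 + 0 = 4, the whole list.

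**Step 2. Compare with the protocol item.** The protocol speaks of changes and does not say which way. That this means both directions is a reading, but the SAP supports it by listing appetite both ways under the same heading. Nothing in either document says why activity should differ.

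**Step 3. Look for another route into the endpoint.**

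- The neighbouring mood endpoint does not help: "Euphoric mood-related events are defined as events coded to the MedDRA PT “euphoric mood". It is a single term and does not describe activity.
- The withdrawal/rebound endpoint (SAP 6.1) also takes in events in patients whose clinical finding was recorded as present. The appetite and activity endpoint has no such link and rests on the term list alone.
- SAP 8.2.3.3 covers body weight and laboratory parameters, not this finding.
- SAP 9 has no listing specific to this item.

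No route exists.

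**Step 4. See where such reactions do appear.**

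- SAP 8.2.3.1: all adverse reactions by system organ class (SOC) and PT, then by seriousness, expectedness, days to onset, action taken and outcome.
- SAP 8.2.3.2: all adverse events by SOC and PT.
- SAP 8.2.3.5: adverse reactions by target disease and by initial dose.
- SAP 9: listings of adverse reactions and of patients with adverse events.

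An increased-activity PT would show up in each of these.

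**Step 5. Size.** First, the plan's own detection figure, as context. SAP 2.1 says that 3400 patients are "expected to have a 97% probability to detect adverse reactions occurring at the incidence of 0.1% or higher in at least 1 patient". With N = 3400 and p = 0.001:

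1 − (1 − 0.001)^3400 = 0.967, which agrees with the stated 97%.

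The documents give no incidence for increased activity, so the number of uncounted reactions cannot be derived. Under assumed incidences, expected patients with such a reaction = N × p:

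- 0.1%: 3400 × 0.001 = 3.4
- 0.5%: 3400 × 0.005 = 17
- 1%: 3400 × 0.01 = 34

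These are upper limits on the shortfall in patients, since someone who also has one of the four listed reactions is counted through that term.

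**The case against.** The best case for leaving the plan alone is that little depends on this grouping. It is not one of the three major investigation items (Protocol 1 and 6.9; SAP 2.2 and 6.1). The protocol's primary safety analysis (7.2.1) is the occurrence and incidence of adverse reactions overall, which the list does not touch. SAP 4.1 calls testing exploratory, SAP 4.2 has no decision rule, and this output is a bare count and proportion. The protocol never says in so many words that both directions are meant, and the SAP never says that this count is its result for the protocol's clinical finding; that link is inferred from the matching wording. Which PTs for raised activity exist, and which belong, cannot be settled from the documents.

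All of that stands, and it limits the point to minor severity. It does not remove the mismatch. The endpoint carries an undirected name, treats its two halves differently, and gives no reason.

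A reader might go further and infer that increased-activity reactions are lost to the survey, or that a 97% chance of seeing a 0.1% reaction falls to zero. The documents do not support that. The 97% is the chance that the survey sees at least one case. It is unchanged here, because such a case still appears in the general tables and listings. Only its entry into this grouping is blocked.

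**Conclusion.** The point holds as a mismatch of definition in a secondary, descriptive safety endpoint. Followed as written, SAP 6.1 gives a figure that includes decreases in activity and excludes increases, under a name and a protocol item that make no such distinction.

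The conclusion rests on two things: reading the undirected protocol wording as covering both directions, which the SAP's handling of appetite supports, and the term list being closed, which the text shows. The size is unknown. It is about 3 to 34 of 3400 patients at assumed incidences of 0.1% to 1%, and zero if no such reaction occurs. It would be tempting to say that the plan is shown to understate the item, but the documents show only that it could. No primary result, test or patient record is affected. Minor severity.

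**What to change.** In SAP 6.1, add the PTs for increased activity that exist in the MedDRA version used, so that activity is covered in both directions as appetite is, and re-run the count in 8.2.3.1. If the restriction to decreases is intended, rename the endpoint so that it says so and give the reason in one sentence.

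The cost is small. Events are already coded to PT for the general tables, so the first option needs a longer term list and one re-tabulation, with no new data collection. Its downside is that a few non-specific terms may enter the group. Separate lines for increase and decrease would keep those visible, but they are optional, since each PT already has its own row in the general table.

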6.2. Efficacy endpoints

- Clinical efficacy: Efficacy of Lyrica at Week 13 will be assessed relative to baseline (including the day of start of treatment).
- Pain score: Patients are asked to rate their pain in the last 24 hours at the time of awakening on an 11-point scale from 0 (no pain) to 10 (worst possible pain).
- Sleep interference score: Patients are asked to rate their intensity of sleep interference in the last 24 hours at the time of awakening on an 11-point scale from 0 (pain does not interfere with sleep) to 10 (pain completely interferes with sleep [could not sleep because of pain]).
- Patients' global impression of change (PGIC): Patients are asked to rate their impression relative to baseline on a 7-point scale from 1 (greatly improved) to 7 (greatly worsened).
1 = greatly improved, 2 = improved, 3 = slightly improved, 4 = unchanged
5 = slightly worsened, 6 = worsened, 7 = greatly worsened
- Clinical global impression of change (CGIC): Investigators rate their impression relative to baseline on a 7-point scale from 1 (greatly improved) to 7 (greatly worsened).
1 = greatly improved, 2 = improved, 3 = slightly improved, 4 = unchanged
5 = slightly worsened, 6 = worsened, 7 = greatly worsened

6.3. Other endpoints

Not applicable.

6.4. Covariates

For safety and efficacy of Lyrica, no covariates or potential covariates are identified from clinical study data, etc. obtained to date.

7. Handling of missing data

If the seriousness/outcome of adverse events and action taken with Lyrica for the adverse events are missing, they will be handled as “unknown” at tabulation.

If body weight is not measured within the acceptable range at each time point (Appendix 1), it will be handled as missing and will not be imputed.

If there is no data of pain score and sleep interference score, it will be handled as missing and will not be imputed in “Week 4” and “Week 13” assessments. If data is missing at Week 13, it will be imputed with the data obtained at the last time point post-dose in “Week 13 LOCF” assessment.

8. Statistical methods and statistical analyses

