2.2. Study objective

The objective of this survey is to collect information on 1) adverse reactions that cannot be predicted from precautions for use (unknown adverse reactions), 2) the incidence of adverse reactions that will occur under actual use conditions, and 3) factors considered to affect safety, efficacy, etc. concerning the safety and efficacy of Lyrica in post-marketing routine clinical practice. At the same time, the necessity of conducting a special investigation or a post-marketing clinical study will be evaluated.

The following events will be evaluated as major investigation items;

- *Peripheral edema and edema-related events**
- *Dizziness, somnolence, loss of consciousness, syncope, and potential for accidental injury*
- *Vision-related events*

**: Adverse events of the cardiovascular and respiratory systems will also be checked.*

3. Interim and final analyses

Interim analyses for periodical safety report will be regularly performed in this survey. Interim analyses will be performed only for items necessary for periodical safety report as specified in this plan. In addition, the final analysis for the application for reexamination will be performed. At the final analysis, all analyses specified in this plan will be performed.

4. Hypothesis and decision rule

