8.1.3. Analysis of binary data

Frequency and its proportion will be calculated. If the confidence interval of proportion is calculated, a 2-sided 95% confidence interval (exact method) will be calculated.

If the proportion is compared between subgroups, Fisher’s exact test and Cochran-Armitage test (exact method) will be performed for the relationships with nominal scale data and ordinal scale data, respectively, and the risk ratio and risk difference with their 95% confidence intervals will be calculated.

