- Elderly patients
- Pediatric patients
- Patients with renal impairment
- Patients with hepatic impairment

Patients with renal impairment are defined as those with “Renal impairment: yes” or creatinine clearance of less than 60 mL/min.

- **Relationship between dosage and administration and development of adverse reactions**

In order to evaluate the relationship between dosage and administration and development of adverse reactions, number and proportion of patients with adverse reactions will be tabulated by SOC and PT for patients whose creatinine clearance and the initial daily dosage are ≥ 60 mL/min and 150 mg, respectively, and patients whose creatinine clearance and the initial daily dosage are ≥ 30 to < 60 mL/min and 75 mg, respectively.

- **Relationship between prior and concomitant medications and development of adverse reactions**

In order to evaluate the relationship between the drug class of prior or concomitant medications and adverse reactions, number of patients with adverse reactions will be tabulated for each PT by target disease (i.e., diagnosis of neuropathic pain) and drug class of prior or concomitant medications. However, concomitant medications used after the initial onset of the event will be excluded from tabulation. For target disease, diseases with number of patients analyzed of approx. 100 or more will be examined.

- **Occurrence of adverse reactions by inclusion in/exclusion from the safety analysis set**

A listing of adverse reactions in patients excluded from the safety analysis set will be prepared. Moreover, number of patients with adverse reactions will be tabulated by SOC and PT.

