8.2.3.4. Subgroup analysis

Number and proportion of patients with at least one adverse reaction will be tabulated by factor specified in Section 5.4. Tests specified in Section 8.1.3 will be performed to evaluate the relationship between patient demographics, etc. and development of adverse reactions. Furthermore, risk ratio and risk difference for the incidence of adverse reactions and their 95% confidence intervals will be calculated between subgroups.

In addition, number and proportion of patients with adverse reactions in each subgroup will be tabulated by SOC and PT for factors showing a significant difference by testing to evaluate the relationship between patient demographics, etc. and development of adverse reactions. Moreover, patient demographics, etc. (including breakdown of past medical history and complications, prior and concomitant medications) will be tabulated in each subgroup and number and proportion of patients with serious adverse reactions will be tabulated by SOC and PT in each subgroup as necessary.

Laboratory parameters will be tabulated as specified in Section 8.2.3.3 in patients whose target disease is painful diabetic neuropathy.

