10.2. Appendix 2: Details of statistical methods

A2.1 Subgroup analysis

Reference populations for calculation of risk ratio and risk difference in subgroup analyses of safety and efficacy are shown below.

Factor	Category	Reference population	Safety/ Efficacy
Special population			
Hepatic impairment	Yes, No	None	Safety, efficacy
Renal impairment	Yes, No	None	Safety, efficacy
Age	Children (<15 years), adults (≥15 to <65 years), elderly (≥65 years)	Adults (≥15 to <65 years)	Safety, efficacy
Patients demographics and others			
Sex	Male, female	Male	Safety, efficacy
Age	<65 years, ≥65 to <70 years, ≥70 to <75 years, ≥75 to <80 years, ≥80 to <85 years, ≥85 years	<65 years	Safety, efficacy
Inpatient/outpatient status at the initial prescription	Inpatient, outpatient	Outpatient	Safety
Body weight (by sex)	<40 kg, ≥40 to <50 kg, ≥50 to <60 kg, ≥60 kg	≥50 to <60 kg	Safety, efficacy
Name of target disease [by disease name]		N/A	N/A
Hemodialysis	Yes, No	None	Safety, efficacy
Creatinine clearance	<15 mL/min, ≥15 to <30 mL/min, ≥30 to <60 mL/min, ≥60 mL/min	≥60 mL/min	Safety, efficacy
Past medical history	Yes, No	None	Safety
Complications	Yes, No	None	Safety
Prior medications	Yes, No	None	Safety, efficacy
Concomitant medications	Yes, No	None	Safety, efficacy
Non-medication therapies	Yes, No	None	Safety
Timing of administration (at the start of treatment)	Before meal, after meal, other	After meal	Safety, efficacy
Daily dose (at the start of treatment)	≤25 mg, >25 to ≤75 mg, >75 to ≤150 mg, >150 to ≤300 mg, >300 to ≤600 mg, >600 mg	>75 to ≤150 mg	Safety, efficacy
Daily dose (maximum)	≤25 mg, >25 to ≤75 mg, >75 to ≤150 mg, >150 to ≤300 mg, >300 to ≤600 mg, >600 mg	>150 to ≤300 mg	Safety, efficacy

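### For adverse reactions the SAP plans only unadjusted one-factor comparisons, although it pairs lower initial dose with lower creatinine clearance, so the dose and renal risk ratios are open to confounding

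*SAP*

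**What the plan says.** One of the objectives in SAP 2.2 is to collect information on "factors considered to affect safety, efficacy, etc. concerning the safety and efficacy of Lyrica". Section 6.4 covers both safety and efficacy and states that "no covariates or potential covariates are identified from clinical study data, etc. obtained to date".

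The method for binary outcomes is in SAP 8.1.3: Fisher's exact test for nominal factors, an exact Cochran-Armitage test for ordinal ones, and "the risk ratio and risk difference with their 95% confidence intervals will be calculated". Section 8.2.3.4 applies this factor by factor: "Number and proportion of patients with at least one adverse reaction will be tabulated by factor specified in Section 5.4", and "risk ratio and risk difference for the incidence of adverse reactions and their 95% confidence intervals will be calculated between subgroups". Section 8.2.3.1 repeats the one-factor testing for the dizziness, somnolence and accidental-injury item. Appendix A2.1 gives each factor a single reference group: clearance of at least 60 mL/min for renal function, and the category above 75 and up to 150 mg for initial daily dose. No stratified or multivariable analysis of reactions appears anywhere. The only covariate in the SAP is the pre-treatment value in the ANCOVA of change (8.1.1), which 8.2.4.6 uses for pain score.

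Section 8.2.3.1 also asks for reactions to be tabulated in two groups. The first is "patients whose creatinine clearance and the initial daily dosage are ≥ 60 mL/min and 150 mg, respectively". The second group has clearance from 30 to below 60 mL/min and starts on 75 mg a day. The dosing text in Protocol section 2 and SAP 2.1 allows dose to be adjusted for age and symptoms.

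**The concern.** If patients with lower clearance tend to start on lower doses, a comparison of dose categories also compares renal function, and a comparison of clearance categories also compares doses. The two doses named in 8.2.3.1 fall in adjacent initial-dose categories of SAP 5.4, and the higher category is the dose reference. The paired clearance classes are likewise adjacent, and the higher one is the clearance reference. So the affected contrasts are ones the plan will report.

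Where both low clearance and higher dose raise risk, the two effects partly cancel. A real dose effect may look weak or absent, and so may a real renal effect. Section 8.2.3.4 produces the detailed follow-up tables only for factors that test significant, so a masked factor would not trigger the tables that might reveal the masking. Age could be involved in the same way, since the dosing text links it to dose.

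**Working it through.** **The plan's own figures.** All three reproduce.
- Probability of at least one case at 0.1% incidence: 1 − 0.999^3400 = 0.967, stated as 97%.
- Vision-related incidence: 380/5134 = 7.40%, with an exact 95% lower bound of 6.70%.
- Expected vision-related cases: 3400 × 0.067 = 227.8, stated as 227 or more.

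None of these concerns the factor analyses. The documents give no reaction rate by dose, clearance or age, so the size of any confounding cannot be derived from them. What follows is an illustration.

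**Assumed inputs.** There are two clearance strata (below 60 mL/min or not) and two initial-dose levels. Let p be the share with clearance below 60 (0.3 to 0.5), o the share in each stratum started on the dose level that the pairing gives to the other stratum (0.1 to 0.3), D = 1.6 the true dose risk ratio (higher against lower), and R the true renal risk ratio at equal dose (1.0 to 2.0). Effects are multiplicative, so base risk cancels.

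**Crude dose risk ratio**

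D × {[(1−p)(1−o) + p·o·R] / [(1−p)(1−o) + p·o]} ÷ {[(1−p)·o + p(1−o)·R] / [(1−p)·o + p(1−o)]}

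- Lowest value, p = 0.5, o = 0.1, R = 2.0: the first brace is (0.45 + 0.10)/0.50 = 1.10 and the second is (0.05 + 0.90)/0.50 = 1.90. Result: 1.6 × 1.10/1.90 = 0.93.
- Highest value with R above 1, p = 0.3, o = 0.3, R = 1.2: the first brace is 0.598/0.58 = 1.031 and the second is 0.462/0.42 = 1.10. Result: 1.6 × 1.031/1.10 = 1.50.

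**Crude renal risk ratio**

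R × [(1−o) + o·D] / [(1−o)·D + o]

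The multiplier on R is 1.06/1.54 = 0.69 at o = 0.1 and 1.18/1.42 = 0.83 at o = 0.3.

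| True renal RR | Crude dose RR (true 1.6) | Crude renal RR |
|---|---|---|
| 1.0 | 1.60 | 0.69-0.83 |
| 1.2 | 1.38-1.50 | 0.83-1.00 |
| 1.5 | 1.16-1.38 | 1.03-1.25 |
| 2.0 | 0.93-1.23 | 1.38-1.66 |

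The crude dose risk ratio falls below 1 only at R = 2.0 with o = 0.1. At R = 2.0 and o = 0.2 it is 1.07-1.08.

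**Second set of assumptions.** Both true risk ratios are 2.0 and 20-35% have clearance below 60. If the lower dose goes to 60% of reduced-clearance patients and 40% of the others, the crude dose risk ratio is 1.75-1.80. At 80% and 40% it is 1.52-1.62, and at 90% and 30% it is 1.32-1.45. At 50% and 50% there is no bias. A Mantel-Haenszel risk ratio returns 2.0 throughout, as it must when the true ratio is constant across strata.

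**Room for a model.** In the SAP's own categories, age (5), sex (1), weight (3), clearance (3), hemodialysis (1) and initial dose (5) use 18 parameters: 227/18 = 12.6 expected vision-related events each. Concomitant medication (1) and one term for each of the eight pain types with a target of about 100 or more would make 27, or 227/27 = 8.4. A collapsed set of age (1), sex (1), weight (1), clearance (3), hemodialysis (1), initial dose (2) and target disease (2) uses 11: 227/11 = 20.6.

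**The case against.** The strongest reply is that the survey is not confirmatory. SAP 4.1 calls all testing exploratory, and the objective is to collect information on factors and judge whether further study is needed. Crude screening fits that aim. The plan also has relevant descriptive checks: the dose-by-clearance tabulation in 8.2.3.1, age, weight, clearance and co-medication by initial-dose group in 8.2.2, demographics within subgroups of significant factors in 8.2.3.4, and a general allowance for further analyses in 8.2.3.5.

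Part of this stands. The tables let a reader see imbalance, and the exploratory label limits what may be claimed. But the joint tabulation covers only the two cells in which dose and clearance move together, so it cannot separate them. The demographic tables yield no adjusted estimate. The exploratory label does not remove bias from a reported risk ratio and its confidence interval.

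A reader might infer more than the documents support:
- That the estimates are in fact confounded, or that patients with low clearance are older and start lower. The pairing in 8.2.3.1 specifies a tabulation and is not data, and the age link rests on the dosing text alone.
- That 6.4 is the reason for the unadjusted tests. The SAP does not say so.
- That the dose effect would vanish or reverse. That happens in one corner of an assumed grid.
- That a model with every listed factor in full is affordable. With target disease by name it is not.

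**Conclusion.** The point holds as a risk that the plan itself makes foreseeable and leaves unaddressed. Reactions get only unadjusted one-factor comparisons, 6.4 recognises no potential covariate, and 8.2.3.1 pairs lower initial dose with lower clearance. The crude dose and renal risk ratios are open to mutual confounding, and those for age possibly so.

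Its size is unknown. For a true dose risk ratio of 1.6 and a renal risk ratio of 1.2 to 2.0, the illustration gives a crude dose value of about 0.93 to 1.50. That range rests wholly on assumed effects, renal share and adherence to the pairing. The dose estimate is unbiased if renal function has no effect on risk, or if dose and clearance are unrelated. No calculation was possible for age. Since factors affecting safety are a stated objective, the change should be made, but the survey's incidence estimates are untouched.

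**What to change.** - Replace SAP 6.4 with a short baseline list: age, sex, body weight, creatinine clearance with hemodialysis, and initial daily dose. Reconcile it with 8.1.1, which already uses the pre-treatment value as a covariate.
- Add to 8.2.3.1 and 8.2.3.4 one exploratory adjusted analysis, fixed in the SAP before it is run, for any adverse reaction and for each of the three major investigation items. Poisson regression with robust variance gives risk ratios directly. Logistic regression also serves if its results are converted to risk ratios. The simplest version is Mantel-Haenszel: dose stratified by clearance, and clearance stratified by dose.
- Use continuous or collapsed terms, for example the three initial-dose groups already in 5.4. If target disease is included, collapse it to postherpetic, other peripheral and central, so that the model suits about 227 vision-related events.
- Report adjusted beside crude risk ratios, and label the crude ones as unadjusted and not as independent effects.
- If missing clearance is handled as its own category, add a complete-case sensitivity analysis.

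The cost is SAP wording and four models on variables already collected. Residual confounding remains where clearance is missing or terms are coarse, and the report should say so.
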